| mild (+) | loss of appetite without alteration in eating habits |
| moderate (++) | oral intake decreased without significant weight loss, dehydration or malnutrition |
| severe (+++) | inadequate oral caloric or fluid intake |

Vomiting:

| | |
|---------------|--------------------------|
| none (-) | |
| mild (+) | 1 episode in 24 hours |
| moderate (++) | 2-5 episodes in 24 hours |
| severe (+++) | ≥ 6 episodes in 24 hours |

After 12 weeks of treatment or thereafter at week 16, 20 or 24 (after 24, 32, 40, or 48 PUVA treatments, respectively) patients with complete remission will be randomized by a computer generated list for treatment allocation into two arms (arm A and B, see below). Patients who haven't experienced complete remission after 24 weeks will discontinue active study participation and will enter an observatory study arm.

Patients with complete response will be randomized to receive either PUVA-maintenance therapy (arm A) or no maintenance therapy (arm B) (Figure 1)

Arm A: oral 8-MOP+UVA

Patients will be treated with PUVA maintenance therapy at constant single UVA doses (UVA-dose will be the same as given in the last treatment session in week 12, 16, 20 or 24 of PUVA therapy). Maintenance treatment will be given once a week for one month (4 weeks), every 2 weeks for 2 months (8 weeks) and after three months once a month over 6 months (Appendix: Figure 1). After 9 (10, 11, or 12) months of maintenance therapy (14 treatments) patients will discontinue therapy. If PUVA treatment does lead to erythema during maintenance therapy, the dose for the next treatment will be reduced by up to 30%.

Patients with recurrence during PUVA maintenance will discontinue the study. After the end of maintenance therapy the patients will be followed up every three months in the first year after treatment, every 6 months in the second year and once a year from year 3 to 5 or until recurrence of the disease.

Arm B: control arm – Patients will receive no therapy. Patients are followed up at the same intervals like patients in study arm A (Appendix: Table 4).

Observatory patient arm:

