13.1. Study design

A randomized placebo controlled clinical trial with 3 to 6 months of PUVA therapy as control and 3 to 6 months PUVA plus 9 months of PUVA maintenance therapy as index therapy. In the Appendix Figure 1 the time-dependent probability of recurrence (“Survival function”) is given for 4 settings.

The primary endpoint of the study is the comparison of median time to recurrence after complete remission between study arm A and study arm B (comparison of curve (1) vs. curve (2), Appendix: Figure 2). A secondary endpoint is the comparison of time from end of treatment to recurrence on condition that the patient is in remission at the end of treatment comparing study arm A and B (end of treatment in study arm A, month 12 to 15; end of treatment in study arm B, month 3 to month 6). This amounts to the comparison between curve (3) and curve (4). After the accrual period patients are observed until the closing date of the study for the main statistical outcome analysis. Patients who have not experienced recurrence by the closing date are considered as censored. Treatment groups are compared by survival analysis (logrank test).

13. 2. Sample size calculations and study duration

Sample sizes were calculated with nQuery Advisor 4.0 software (www.statistical-solutions-software.com). The assumptions were $\alpha=0.05$, $\text{power}=0.8$, one(two)-sided logrank test and an accrual time of 2 years.

According to an earlier study at the dermatologic clinic the median time to recurrence after PUVA therapy was 1 year. An exponential survival function with parameter $\lambda_1=0.7$ was chosen for controls, giving a median time to recurrence of 1 year.

The alternative hypothesis (i.e. the minimum clinically relevant treatment effect) was chosen to be exponential with $\lambda_2=0.35$ (relative hazard 2, median time to recurrence 2 years) for the primary treatment effect. The overall duration of the study (to enrol 55 patients assuming an accrual period of 2 years) until closing date for the main statistical outcome analysis was assumed to be four years (accrual phase, 24 months; initial PUVA treatment of last patient enrolled, 3 months; PUVA maintenance treatment in last patient enrolled, 9 months; minimum follow-up period, 12 months). Scenario D1 and D4 refer to these assumptions. Independent of the closing date for the main statistical outcome analysis the maximum follow-up in an individual patient will be 60 months.

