| | Primary endpoint | | | | Secondary endpoint | | | |
|---|------------------|-----------|-----------|-----------|--------------------|-----------|-----------|-----------|
| | D1 | D2 | D3 | D4 | D5 | D6 | D7 | D8 |
| Test significance level | 0.05 | 0.05 | 0.05 | 0.05 | 0.05 | 0.05 | 0.05 | 0.05 |
| 1 or 2 sided test? | 2 | 1 | 2 | 1 | 2 | 1 | 2 | 2 |
| Length of accrual period | 2 | 2 | 3 | 3 | 2 | 2 | 3 | 3 |
| Maximum follow up | 3.75 | 3.75 | 4.75 | 4.75 | 3 | 3 | 4 | 4 |
| Control hazard λ_1 | 0.7 | 0.7 | 0.7 | 0.7 | 0.7 | 0.7 | 0.7 | 0.7 |
| Maintenance hazard λ_2 | 0.35 | 0.35 | 0.35 | 0.35 | 0.35 | 0.35 | 0.35 | 0.35 |
| Hazard ratio, $h=\lambda_1 / \lambda_2$ | 2 | 2 | 2 | 2 | 2 | 2 | 2 | 2 |
| Power (%) | 80 | 80 | 80 | 80 | 72 | 73 | 74 | 76 |
| n per group | 47 | 37 | 44 | 35 | 47 | 37 | 44 | 35 |
| Accrual per year (2 Treatments) | 48 | 38 | 32 | 26 | 48 | 38 | 32 | 26 |

For the secondary endpoint (recurrence after 9 months of maintenance therapy vs. recurrence after standard therapy only) essentially the same scenario was assumed: exponential survival, hazard ratio 2. Only the length of follow up was shortened by 0.75 years. In this regard not power but sample size was fixed and the power was variable. Scenario D5 to D8 relate to these assumptions.

Finally scenario D2 was chosen. 37 patients per group are required (41 patients if accounting for 10% loss to drop-out, non-compliance and/or follow-up).

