13.3. Randomization procedure

After a maximum of 24 weeks (48 PUVA treatments) patients without complete remission will discontinue active study participation but they will be followed up in an observatory arm. Patients with complete remission after 12 weeks (24 PUVA treatments), 16 weeks (32 PUVA treatments), 20 weeks (40 PUVA treatments) or maximum of 24 weeks (48 PUVA treatments) will be randomized by a computerized randomization service to receive either PUVA-maintenance therapy (*Arm A*) or no maintenance therapy (*Arm B*) (Appendix: Figure 1). Randomization will be done using Randomizer, Medical University of Graz, Austria (<https://www.randomizer.at/random>).

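### Section 13.2 plans to enrol 55 patients in two years, which cannot supply the 74 randomised patients (82 with loss) required by the scenario it adopts

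*Combined protocol and SAP*

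**What the plan says.** All the figures at issue are in section 13.2.

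- The duration paragraph reads "The overall duration of the study (to enrol 55 patients assuming an accrual period of 2 years". It adds up to four years: 24 months of accrual, 3 of induction ("initial PUVA treatment of last patient enrolled, 3 months"), 9 of maintenance and 12 of minimum follow-up. It ends with "Scenario D1 and D4 refer to these assumptions".
- The scenario table gives four primary-endpoint scenarios, D1 to D4, with 47, 37, 44 and 35 patients per group. The accrual rows read "Length of accrual period | 2 | 2 | 3 | 3" and "Accrual per year (2 Treatments) | 48 | 38 | 32 | 26". Maximum follow-up is 3.75 years for D1 and D2, and 4.75 years for D3 and D4.
- The section closes: "Finally scenario D2 was chosen. 37 patients per group are required (41 patients if accounting for 10% loss to drop-out".

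Sections 5 and 13.3 state who is randomised. Induction lasts 12 to 24 weeks, and only patients in complete remission go on to arm A or B. Section 13.3 says: "After a maximum of 24 weeks (48 PUVA treatments) patients without complete remission will discontinue active study participation". Section 5 says the same, and sends these patients to the observatory arm.

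**The concern.** The section gives two incompatible recruitment figures for the same two years: 55 patients, and the 74 (or 82) that D2 requires. The usual explanation for such a gap, that one figure counts patients enrolled and the other patients randomised, makes matters worse here. Enrolment comes before a selection step, so the enrolled number must be the larger of the two, and it is the smaller.

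If a site, monitor or ethics committee took 55 as the target, the stated 80% power would be out of reach. The documents also give no complete-response rate. The number who must start induction to yield 74 to 82 responders therefore cannot be worked out, and it cannot be judged whether two years is enough to recruit them.

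**Working it through.** **Inputs (section 13.2).** Exponential recurrence hazards of 0.7 (control) and 0.35 (maintenance) per year, hazard ratio 2; one-sided 5% log-rank test (D2); accrual A = 2 years; maximum follow-up T = 3.75 years. Uniform accrual and no loss are assumed.

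**1. Probability of an observed recurrence.** P = 1 − [exp(−λ(T−A)) − exp(−λT)] / (λA).

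- Control: 1 − (0.2938 − 0.0724)/1.4 = 0.842
- Maintenance: 1 − (0.5420 − 0.2691)/0.7 = 0.610
- Mean: 0.726

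**2. Does D2 reproduce?** (1.645 + 0.842)² = 6.18.

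- Schoenfeld: 4 × 6.18/(ln 2)² = 51.5 recurrences; 51.5/0.726 = 70.9 patients
- Freedman: 6.18 × [(2+1)/(2−1)]² = 6.18 × 9 = 55.6 recurrences; 55.6/0.726 = 76.6 patients

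The plan's 74 lies between the two, so D2 is sound.

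**3. Can 55 be matched to any scenario?** The totals for D1 to D4 are 2 × 47, 37, 44 and 35 = 94, 74, 88 and 70. Neither a total nor a per-group number equals 55. Over two years, 55 is 27.5 per year, against 38 per year (76 in two years) in the D2 column.

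**4. Shortfall.** 74 − 55 = 19 and 82 − 55 = 27. To reach the target, each enrolled patient would have to supply 74/55 = 1.35 or 82/55 = 1.49 randomised patients, which is impossible.

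**5. Power if recruitment stopped at 55, all randomised and none lost.** With d recurrences, power is Φ(√d/3 − 1.645) by Freedman and Φ((√d/2) ln 2 − 1.645) by Schoenfeld.

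| Randomised | Expected recurrences | Freedman | Schoenfeld | Simulated log-rank |
|---|---|---|---|---|
| 74 | 74 × 0.726 = 53.7 | 0.788 | 0.815 | 0.810 |
| 55 | 55 × 0.726 = 39.9 | 0.678 | 0.707 | 0.700 |

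Keeping the control hazard at 0.7, the hazard ratio detectable with 55 patients at 80% power is 2.22 (Schoenfeld) to 2.34 (Freedman), instead of 2. A 10% loss from 55 leaves 49.5 patients and power of 0.64 to 0.67.

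**6. Effect of non-response.** No response rate is given, so this is an assumed range. With 60% to 90% complete response, 55 enrolled would give 33 to 49.5 randomised and power of about 0.50 to 0.67. Randomising 74 would need about 82 to 123 enrolled; randomising 82 would need about 91 to 137.

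**7. Cross-reference.** The timetable is 24 + 3 + 9 + 12 = 48 months. Less 3 months of induction, this is 45 months, or 3.75 years. That matches D1 and D2. D4 has 3-year accrual and 4.75-year follow-up, so it does not match, and the adopted D2 is not cited.

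**The case against.** The best defence is that the sample size is not in doubt. The section ends with a clear choice of D2, the D2 accrual rate of 38 per year is consistent with it, and 55 sits in a parenthesis about duration. Nothing makes 55 a cap or a stopping rule, so the power loss is conditional. This is right as far as it goes: the required number randomised is settled, and the fall to about 70% applies only if recruitment stops at 55. But 38 per year is a rate for patients entering the two arms. The only stated count of patients to enrol is still 55, and it cannot supply D2.

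A second argument is that 55 may be a mislabelled number of recurrences, since D2 needs 51.5 to 55.6 and expects 53.7. That is plausible, and the power concern would then fall away. However, the text says patients are to be enrolled, and nothing in the documents supports the other reading.

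Third, the citation of D1 and D4 may be a slip for D1 to D4, because D5 to D8 are cited together for the secondary endpoint. D3 and D4 would still contradict the two-year accrual.

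Two smaller points stand without changing the result. Strictly, 37/0.9 = 41.1 rounds up to 42 per group (84 in total); the plan's 41 fits 37 × 1.1 = 40.7. And the timetable counts 3 months of induction although up to 24 weeks is allowed.

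**Conclusion.** The concern holds. Read as patients, 55 is wrong as written: it is at least 19 below the number D2 must randomise, 27 below the loss-adjusted number, and the real gap is larger by however many patients do not reach complete remission. The D2 calculation is correct. The fault lies in the enrolment figure, the recruitment rate it implies, and the scenario reference.

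If 55 were the true limit, one-sided power for the primary endpoint would be at most about 70%, not 80%. This rests on the plan's own hazards, accrual and follow-up, on uniform accrual, and on the best case of full response and no loss. The point needs correcting before the plan is relied on, because a stated recruitment figure in the sample-size section cannot deliver the stated power.

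**What to change.** - Replace the figure of 55 with the D2 numbers: 74 randomised, or 82 (41 per group) with the stated 10% loss. State explicitly that 41 is per group.
- Add the number who must start induction PUVA: 82 divided by a stated and sourced complete-response rate. Confirm that this number can be recruited in two years.
- If 55 is the real recruitment limit, keep it and restate the primary power as at most about 70% one-sided, lower once non-response and loss are counted.
- If 55 was meant as a number of recurrences, label it so.
- Change the scenario reference to D1 and D2, the primary scenarios with two-year accrual and 3.75-year follow-up.

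The cost is a few words, one sourced rate and a feasibility check. This point does not require a change to the 48-month timetable unless that check shows two years is too short. Keeping 55 costs a less favourable power statement.

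### The secondary-endpoint power (D5–D8) keeps every arm A patient and shortens follow-up in both arms; on the plan's own hazard D6 has about 70% power, not 73%, and D8 is mislabelled two-sided

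*Combined protocol and SAP*

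**What the plan says.** Sections 3.2 and 13.1 start the secondary endpoint's clock when treatment ends and stop it at recurrence, with this restriction: "on condition that the patient is in remission at the end of treatment comparing study arm A and B". Section 13.1 puts end of treatment at month 12 to 15 in arm A and at month 3 to 6 in arm B. For arm B that is the time of randomization. The description of Appendix Figure 2 in Section 13 expects some recurrences while maintenance is under way.

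Section 13.2 gives four scenarios for the primary endpoint (D1–D4) and four for the secondary (D5–D8). The secondary block keeps the hazards (0.7 control, 0.35 maintenance) and the numbers per group (47, 37, 44, 35). The text explains: "Only the length of follow up was shortened by 0.75 years" and "In this regard not power but sample size was fixed and the power was variable". The follow-up row of the table is "Maximum follow up | 3.75 | 3.75 | 4.75 | 4.75 | 3 | 3 | 4 | 4", with one value per scenario and no distinction by arm. The sidedness row is "1 or 2 sided test? | 2 | 1 | 2 | 1 | 2 | 1 | 2 | 2".

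Stated power is 72%, 73%, 74% and 76% for D5 to D8. D2 was chosen (37 per group, one-sided), so D6 is its secondary-endpoint partner. The increase from 37 to 41 per group is for drop-out, non-compliance and loss to follow-up.

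**The concern.** The power inputs do not match the endpoint's definition, in two ways that pull in opposite directions.

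- **Arm A size.** A patient who recurs during the nine months of maintenance cannot be in remission at its end. Keeping all 37 overstates the arm A events and so the power. The 10% allowance does not cover this loss, because recurrence is neither drop-out nor loss to follow-up.
- **Arm B follow-up.** The arm B clock starts at randomization for both endpoints, so its maximum follow-up stays at 3.75 years. Cutting it to 3 understates the arm B events and the power.

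D8 raises a separate question that needs no software. As labelled, D7 and D8 share significance level, sidedness, accrual, follow-up and hazards. D8 has fewer patients (35 against 44 per group) but more stated power (76% against 74%). Both columns cannot be right.

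What is at stake is the accuracy of a power that the protocol states for a named endpoint.

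**Working it through.** **Inputs (Section 13.2).** Significance level 0.05; one-sided for D2 and D6; hazards λ_A = 0.35 and λ_B = 0.7 per year; accrual A = 2 years, taken as uniform; maximum follow-up T = 3.75 years (D2) or 3 years (D6); 37 per group.

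**Formulas.**
- Probability of an observed event: p = 1 − [exp(−λ(T−A)) − exp(−λT)]/(λA). Expected events: E = n·p.
- Log-hazard power: Φ(ln 2/√(1/E_A + 1/E_B) − z), with z = 1.645 one-sided and 1.960 two-sided.
- Exponential (Lachin–Foulkes) power: Φ([|λ_A − λ_B|√N − z√V0]/√V1). Here N is the total number of patients, q_A and q_B are the fractions of N in each arm, and V1 = λ_A²/(q_A p_A) + λ_B²/(q_B p_B). V0 has the same form with the weighted mean hazard in both arms.

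**Step 1: reproduce the plan.** D2 gives 80.6% (log-hazard) and 79.3% (exponential), against 80% stated. For D6 with 37 v 37 and T = 3 in both arms:
- p_A = 0.493 and p_B = 0.733, so E_A = 18.2 and E_B = 27.1.
- ln 2/√(1/18.2 + 1/27.1) = 2.289, and Φ(2.289 − 1.645) = 74.0%. The exponential formula gives 73.3%.

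The stated 73% therefore comes from keeping all 37 arm A patients and shortening both arms.

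**Step 2: arm A patients who qualify.** exp(−0.35 × 0.75) = 0.769, and 37 × 0.769 = 28.5. Under the exponential assumption this selection leaves the later hazard unchanged and only removes patients.

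**Step 3: correct D6.** Arm A: 28.5 patients, T = 3, E_A = 28.5 × 0.493 = 14.0. Arm B: 37 patients, T = 3.75, p_B = 0.842, E_B = 31.2. Then ln 2/√(1/14.0 + 1/31.2) = 2.156, and Φ(2.156 − 1.645) = 69.5%.

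| D6, one-sided 0.05 | Log-hazard | Exponential | Simulated logrank (20,000 runs) |
|---|---|---|---|
| As planned: 37 v 37, T = 3 both | 74.0% | 73.3% | 75.1% |
| Arm B follow-up corrected only | 76.0% | 76.5% | not run |
| Arm A size corrected only | 67.8% | 66.8% | 68.3% |
| Both corrected | 69.5% | 69.7% | 71.1% |

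**Step 4: sensitivity to recurrence during maintenance (other inputs as in Step 3).** The plan states no recurrence rate for this period, so other values are assumptions.

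| Arm A recurring | Log-hazard | Exponential |
|---|---|---|
| 10% | 73.5% | 73.9% |
| 15% | 72.1% | 72.4% |
| 23% (from hazard 0.35) | 69.5% | 69.7% |
| 40% | 62.9% | 62.0% |

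**Step 5: D8.** With 35 v 35, A = 3 and T = 4, E_A = 19.7 and E_B = 27.7, so ln 2/√(1/19.7 + 1/27.7) = 2.354.
- Two-sided: Φ(2.354 − 1.960) = 65.3%; exponential 64.3%.
- One-sided: Φ(2.354 − 1.645) = 76.1%; exponential 74.9%.

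The stated 76% matches only the one-sided test, and D4, the primary-endpoint partner with 35 per group, is one-sided. With the Step 3 corrections (arm A 35 × 0.769 = 26.9; arm B T = 4.75; E_A = 15.2, E_B = 30.7), one-sided D8 gives 71.4% and 70.6%, about 71%.

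**Step 6: D5 and D7, corrected the same way, two-sided.** D5 falls from 72% to 68.1% by both formulas. D7 falls from 74% to 69.7% (log-hazard) and 68.7% (exponential).

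**The case against.** The strongest reply is that the gap is small and decides nothing. The number of patients is set by the primary endpoint. The plan says openly that secondary power was left to fall where it would, and already puts it below 80%. The two simplifications partly cancel. Different approximations for the uncorrected D6 already range from 72.6% (Freedman) to 75.5% (Schoenfeld). All of that stands and keeps this a minor point. It does not rescue the 73%: each method gives a lower figure once arm A is reduced and arm B follow-up restored.

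The 77% retention is derived, not stated. If only 10% of arm A recurs during maintenance, 73% is about right. That also stands, and is why the assumption needs to be written down. A larger assumption lies behind it: that the hazard ratio of 2 persists after maintenance stops. With a post-treatment arm A hazard of 0.45 instead of 0.35, the log-hazard formula gives about 42%. The correction makes the stated figure consistent with the plan's inputs; it does not make those inputs more certain.

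The spare patients do not close the gap. With all 41 per arm retained, simulation gives 74.7% with both corrections, but those patients are reserved for the 10% loss.

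Three stronger readings might be inferred, and the documents do not support them.
- *Power of 67–68% or lower.* That needs arm B follow-up cut by 0.75 years, which contradicts the arm B end of treatment in Section 13.1.
- *A two-sided power for D6 in place of the stated one.* D6 is explicitly one-sided. Whether one-sided testing is suitable is a separate question.
- *An undersized trial, or a null secondary result that would be badly misread.* D2 reproduces, and a difference of about 3 points would hardly change how a null result is read.

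**Conclusion.** The point holds, as a minor error. D5–D8 use an arm A size and an arm B follow-up that do not fit the endpoint as defined. For D6 the result is about 70% one-sided instead of 73%, a shortfall of about 3 points. This rests on exponential recurrence, uniform accrual, hazard 0.35 both during and after maintenance, and hazard 0.7 in controls. With 10% recurrence during maintenance the shortfall disappears; with 40% power is about 62–63%.

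D8 cannot be right as labelled. Its 76% is a one-sided figure, and the two-sided power with the same inputs is 64–65%. D8 was not the chosen scenario, so this is an error in the table without consequence for the design.

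Neither point touches the primary-endpoint calculation or the number to be randomized.

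**What to change.** In Section 13.2:

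1. Recompute D5–D8 with arm A multiplied by exp(−0.35 × 0.75) = 0.769 and follow-up shortened by 0.75 years in arm A only. The table then needs separate arm A and arm B values for number of patients and maximum follow-up.
2. State the assumption: the maintenance hazard of 0.35 per year applies during maintenance, so about 23% of arm A recurs before the secondary endpoint's clock starts. Give the power at 10% recurrence beside it (about 73–74% for D6).
3. Restate D6 as about 70% one-sided. D5 becomes about 68% and D7 about 69–70%, both two-sided.
4. Relabel D8 as one-sided, with a recomputed power of about 71%.

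The cost is a recalculation and a few words in the table and text. No patients, visits or design features change.

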13.3. Randomization procedure

After a maximum of 24 weeks (48 PUVA treatments) patients without complete remission will discontinue active study participation but they will be followed up in an observatory arm. Patients with complete remission after 12 weeks (24 PUVA treatments), 16 weeks (32 PUVA treatments), 20 weeks (40 PUVA treatments) or maximum of 24 weeks (48 PUVA treatments) will be randomized by a computerized randomization service to receive either PUVA-maintenance therapy (*Arm A*) or no maintenance therapy (*Arm B*) (Appendix: Figure 1). Randomization will be done using Randomizer, Medical University of Graz, Austria (<https://www.randomizer.at/random>).

14. ETHICAL AND LEGAL ASPECTS

Acknowledgement / approval of the study

Approval from the ethics committee (EC) must be obtained before starting the study.

The clinical trial shall be performed in full compliance with the legal regulations according to the Drug Law (AMG - Arzneimittelgesetz) of the Republic of Austria.

An application must also be submitted to the Austrian Competent Authorities (CA) (Bundesamt für Sicherheit im Gesundheitswesen (BASG) represented by the Agency for Health and Food Safety (AGES PharmMed) and registered to the European Clinical Trial Database (EudraCT) using the required forms. The timelines for (silent) approval set by national law must be followed before starting the study.

Changes in the Conduct of the Study

Protocol amendments

Proposed amendments must be submitted to the appropriate CA and ECs. Substantial amendments may be implemented only after CA/EC approval has been obtained. Amendments that are intended to eliminate an apparent immediate hazard to subjects may be implemented prior to receiving CA/EC approval. However, in this case, approval must be obtained as soon as possible after implementation.

Study Termination

If the sponsor or the investigator decides to terminate the study before it is completed, they will notify each other in writing stating the reasons of early termination. In terminating the study, the sponsor and the investigator will ensure the adequate consideration is given to the protection of the subject interests. The investigator, sponsor or (designated CRO on behalf of the sponsor) will notify the relevant CA and EC. Documentation will be filed in the Trial Master and Investigator Files.

Clinical Study Report (CSR)

Within one year after the final completion of the study, a full CSR will be prepared by the sponsor and submitted to the EC and the competent authority.

16. References

Diederer PV, van Weelden H., Sanders CJ, et al : Narrowband UVB and psoralen-UVA in the treatment of early-stage mycosis fungoides: a retrospective study. J Am Acad Dermatol 2003; 48: 215-19.

